4.4.1 Randomization procedure

At screening, participants will be assigned an identification number on a first-come, first-served basis. When it is confirmed that the participant is eligible for the clinical trial, he/she will be randomized.

The assignment of each participant to a particular treatment arm (experimental and control group will be performed in a 1:1:1:1 ratio) will be done by using an electronic system, which is centrally administered.

Near Infrared Transcranial Laser Therapy in Subjects with Major Depressive Disorder: A study of Dosing with Laser.

For each participant at each visit, the investigator or center coordinator will communicate with the central statistician and, through a user and password assigned for the center, will enter the web system where he/she will be able to request and obtain the corresponding treatment number assigned to him/her in the study, and then proceed with the laser application. The participants and the study investigator will be blinded to the treatment assignment. The screen of the medical device does not show information of the dose applied to each participant, only the group to which he/she belongs will be referenced, keeping the dosing details confidential.

At central level, the unblinded statistician (responsible for administering this web system) will know which treatment arm corresponds to each participant from each research center.

4.4.2 *Blinding procedure*

This study is a clinical trial where blinding of both the investigator and the study participant will be assured. Only the treatment identifiers, the central statistician of the study, will know the treatment identifiers.

The sponsor is responsible for providing the medical device under study, programming and maintenance of the device.

The investigator at each center will be responsible for providing the corresponding dose according to the intervention under study (treatment assigned by the statistician through the web system) to each study participant.

Simulation blinding will be effective because the radiation is not visible and because no dose from the NIR-TLT will produce any perceptible difference from the simulation patient, e.g., skin heating.

4.4.3 *Contingency plan for opening of the blind*

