4.6 Subject Numbering

Subjects enrolled in the ELATED-4 study will be identified by subject numbers 01 through 150 (to account for selection failures and drop-out prior to randomization).

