4.9 Study Visits

The study includes screening tests, treatment and a series of follow-up visits.

4.9.1 Selection Visit - Week 0

Purpose

The purpose of the screening visit will be to determine the eligibility of patients to participate in the study.

Procedures

Study personnel will consent subjects to the study, perform a psychiatric evaluation, and screen for the presence of MDD using the MINI, QIDS-C, and CGI-S scales.

Laboratory tests (including urine collection for urine biochemical analysis and urine toxin analysis (also called Urine Drug Screen), urine pregnancy test, and a complete physical examination including vital signs and weight will be performed.

Approximately 15 cc \pm 5 cc (15 ml) of blood will be drawn for laboratory safety testing. To confirm that a patient is healthy enough to participate, a complete blood work-up with differentials, thyroid stimulating hormone test, blood biochemistry (glucose, calcium, sodium, potassium, carbon dioxide, chlorine, albumin, total protein, alkaline phosphatase, transaminases, total and fractionated bilirubins, urea, creatinine) and a high sensitivity C-reactive protein test will be performed. A PET scan will be performed on patients within the study subgroup to meet the exploratory objective.

Near Infrared Transcranial Laser Therapy in Subjects with Major Depressive Disorder: A study of Dosing with Laser.

Once all tests and procedures are available for review, study personnel will determine subject eligibility based on all inclusion and exclusion criteria.

Subjects who report having taken antidepressants at the screening examination may choose to continue medication during the study or taper and discontinue therapy prior to the baseline visit (under the supervision of a treating doctor). However, subjects who have discontinued more than two antidepressants in the current episode of depression will be excluded.

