The NIR-TLT delivery is expected to last no longer than 7.15 minutes (429 seconds) in total (simultaneous application to the left and right forehead). The subject will be allowed to rest for 5 minutes after NIR-TLT delivery. The skin at the application sites will be inspected again after laser application. A log will be kept with the dates of delivery of the NIR-TLT.

Near Infrared Transcranial Laser Therapy in Subjects with Major Depressive Disorder: A study of Dosing with Laser.

treatment per study subject. The use of cell phones, tablets, computers or electronic devices will not be allowed during laser administration.

[figure not shown]
During treatment visits and prior to NIR-TLT, study personnel will collect tolerability (safety) and efficacy data:

1. Safety data: SAFTEE-SI (self-assessed), C-SSRS, adverse events and concomitant medication form.
2. Efficacy data - HAMD-17.

In addition to the evaluation described above, during visits 1, 9 and 18:

Prior to the NIR-TLT study, the staff will collect primary efficacy data from metric measurements and brain electrophysiology data:

1. Efficiency data:
 - a. Doctor-administered scales (1): HAMD-17, QIDS-C and CGI-S.
 - b. Patient-Reported Scales (1): ASQ and SDQ
2. Brain Electrophysiology Data - Study personnel will conduct a first 10-minute EEG recording session, treat the patient according to their NIR-TLT group randomization, and then conduct a second 10-minute EEG recording session as soon as possible after the end of treatment, but within 15 minutes.

3. Exploratory PET scan data: A PET scan will be performed on the participants selected to be part of the research subgroup, before the first treatment visit and within 24 hours of the end of the last intervention (visit 18).

4.9.3 Follow-up visit (Post Treatments) - Week 8

Near Infrared Transcranial Laser Therapy in Subjects with Major Depressive Disorder: A study of Dosing with Laser.

The next visit will occur two weeks after the last cerebral blood flow impact visit.

Purpose: The purpose of the follow-up visit is to evaluate the long-term antidepressant effect of NIR-TLT.

Procedures: During the follow-up study, staff will collect tolerability (safety) and efficacy data:

1. Safety data: SAFTEE-SI (self-assessed), adverse events and concomitant medication form.

2. Efficiency data:

- a. Doctor-administered scales (1): HAMD-17, QIDS-C and CGI.
- b. Patient-reported scales (1): SDQ and ASQ.

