In addition, the frequency and severity of side effects and adverse events reported for each dose will be compared using a Fisher's exact test. The corrective actions taken by the doctors as well as the clinical judgment on the likelihood of association of the side effect/adverse event with the NIR-TLT dose will also be reported.

D. Findings visualized in the PET scan:

The analysis of the results obtained in the PET will be for exploratory purposes to study the brain metabolism of the participants, before and at the end of the study intervention in the 4 groups. Following the recommendations of Daniel et al. (Daniel, 2012), for the exploratory analysis we will work with a minimum number of 5 participants per group, with a total of 20 participants.

The results obtained in the PET will be presented in a descriptive manner.

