

77. Zivin, J. A., Albers, G. W., Bornstein, N., Chippendale, T., Dahlof, B., Devlin, T., ... & Kasner, S. (2009). Effectiveness and safety of transcranial laser therapy for acute ischemic stroke. *Stroke*, 40(4), 1359-1364.3.

8. Table of Assessments

STUDY WEEK	Week 0	Week 1	Week 1 to 3	Week 3	Week 4 to 6	Week 6	Week 8
VISIT PROCEDURE	V0 Selection	V1	V2 to 8	V9	V10 to 17	V18	V19 Follow-up
Consent	■						
M.I.N.I.	■						
PET scan in study subgroup	▲					▲	
Concomitant Medication	■	■	■	■	■	■	■
Physical Examination / Lab	■ / ▲						■
Progress Note		■	■	■	■	■	■
Vital Signs	■	■	■	■	■	■	■
Adverse Events Form		■	■	■	■	■	■
ASQ	● / ▲	● / ▲	● / ▲	● / ▲	● / ▲	● / ▲	● / ▲
CGI	■	■		■		■	■
C-SSRS	■	■	■	■		■	■
HAMD-17	■	■		■		■	■
QIDS-C	■	■		■		■	■
SAFTEE-SI	● / ▲	● / ▲	● / ▲	● / ▲	● / ▲	● / ▲	● / ▲
SDQ	● / ▲	● / ▲	● / ▲	● / ▲	● / ▲	● / ▲	● / ▲
EEG		■		■		■	
Treatment- tx		▲	▲	▲	▲	▲	

Legend

- DOCTOR
- ▲ RESEARCH ASSOCIATE
- PATIENT

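### Section 4.9.1 and the Table of Assessments place the baseline PET before eligibility and randomisation, section 4.9.2 sets a looser window, and nothing stated secures 5 per group among 20

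*Protocol*

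**What the plan says.** **Target.** Section 5.5 D, on the PET findings: "we will work with a minimum number of 5 participants per group, with a total of 20 participants". The results are to be presented descriptively, and sections 1 and 4.1 class the aim as exploratory.

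**Timing of the first scan.** Three places speak to it:
- Section 4.9.1 (Selection Visit, Week 0) includes it among the procedures: "A PET scan will be performed on patients within the study subgroup to meet the exploratory objective". The paragraph that follows reads "Once all tests and procedures are available for review, study personnel will determine subject eligibility based on all inclusion and exclusion criteria".
- The Table of Assessments (section 8) has a row "PET scan in study subgroup", marked at V0 Selection and at V18.
- Section 4.9.2, item 3, places the two scans "before the first treatment visit and within 24 hours of the end of the last intervention (visit 18").

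**Order of allocation.** Section 4.4.1: "When it is confirmed that the participant is eligible for the clinical trial, he/she will be randomized". The ratio is 1:1:1:1 through a centrally run electronic system. No blocking, stratification or quota by PET membership is mentioned.

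**Loss before randomisation.** No rate is given. Section 4.6 has subjects "identified by subject numbers 01 through 150", a range meant to cover both selection failures and drop-out before randomisation, against 112 randomised.

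**The concern.** Section 4.9.1 puts a radioactive-tracer scan ahead of the decision on whether the person can enter the trial, although the scan is not used to decide eligibility. Two consequences follow if sites work to that section and the Table.

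- Someone scanned and then found ineligible has had an 18F-FDG PET/CT that contributes nothing to the before-and-after description.
- The subgroup is fixed before the arm is known. The number per arm is then whatever the randomisation produces, whereas section 5.5 D names a number per arm. An arm with only two or three scanned people would give a thin description.

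Visit placement is a conduct matter that the protocol settles itself, and here it settles it in two ways. The stakes are avoidable exposure and an unsecured subgroup count. No hypothesis test, power figure or error rate depends on PET.

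**Working it through.** **1. The plan's own figure.** 4 groups × 5 = 20, which reproduces. If 5 is a minimum and 20 is the total, each arm must have exactly 5.

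**2. Sequence under each passage.**
- Section 4.9.1 with section 4.4.1: scan, then eligibility, then randomisation, then visit 1.
- Section 4.9.2: scan at any time before visit 1, so the order eligibility, randomisation, scan, visit 1 is also allowed.
- Table of Assessments: scan under V0. There is no column between V0 and V1.

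**3. Chance of 5 in every arm if 20 people are scanned first and all are randomised.** The randomisation method is an assumption in every case.
- Simple 1:1:1:1: 20!/((5!)^4 × 4^20) = 0.0107, or 1.1%. By simulation the smallest arm averages 2.8 and has 3 or fewer in about 75% of cases.
- The 20 as a random draw from arms fixed at 28: C(28,5)^4 / C(112,20) = 0.0143, or 1.4%. The smallest arm averages 3.0 and has 3 or fewer in about 69% of cases.
- Blocks of 4, one centre, 20 consecutive people: five complete blocks, so 5/5/5/5 is certain.
- Blocks of 8, one centre, 20 consecutive people: two complete blocks give 4 per arm, and the 4 people in the part-block must fall one per arm: 2^4 / C(8,4) = 16/70 = 23%.
- Blocks of 4, two centres of 10 each: complete blocks give 4 per arm, and the two part-blocks of 2 must complement each other: 1/C(4,2) = 1/6 = 17%.

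In the blocked cases the smallest arm never falls below 4.

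**4. Scans of people never randomised.** With loss q before randomisation, 20 randomised people need 20/(1 − q) baseline scans on average.

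| Assumed q | Scans needed | Unused |
|---|---|---|
| 5% | 20/0.95 = 21.1 | about 1 |
| 10% | 20/0.90 = 22.2 | about 2 |
| 25.3% | 20/0.747 = 26.8 | about 7 |

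The last row treats the numbering allowance as a rate: (150 − 112)/150 = 38/150 = 25.3%. If exactly 20 are scanned at selection, the chance that all are randomised is 0.95^20 = 35.8% at 5% loss and 0.90^20 = 12.2% at 10%.

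**5. People scanned or scan pairs.** If the 20% loss used in section 5.3 applied to the subgroup (an assumption), 20 baseline scans would give 20 × 0.8 = 16 pairs. To expect 5 pairs per arm, 5/0.8 = 6.25, so 7 per arm, or 28 baseline scans. Section 5.5 D does not say which count it means.

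**The case against.** **Timing.** Section 4.9.2 speaks of participants already selected for the subgroup and sets only a limit before the first treatment visit. The Table has no column between V0 and V1, so a scan after randomisation might be entered under V0 for want of a better place. On this view the order within week 0 is not fixed. That stands in part. It makes the matter a conflict between passages, not a settled instruction to scan ineligible people. But section 4.9.1, read in order, does put the scan before the eligibility decision, and a site following it would do so.

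**Count.** The 1% needs simple randomisation and exactly 20 people scanned. Sections 1 and 4.4 describe equal groups of 28, which makes some restriction on allocation plausible, and block details are commonly kept out of a protocol. Their absence is no fault. With blocks the imbalance could be nil or one person. The wording could also mean that 20 is simply what a minimum of 5 implies, and a site could go on scanning until each arm has 5, though that would normally exceed 20. All of this stands. A reader might infer that the plan cannot deliver 5 per group, or almost never would; the document does not support that. It supports only that nothing stated ensures it.

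**Loss rate.** A reader might take 25% as the expected screen-failure rate. It is a numbering range that also covers drop-out, and it need not apply to a subgroup that could be chosen late in screening.

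**Weight.** The aim is exploratory and descriptive. A split of 4/5/5/6 would change no conclusion. That stands.

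**Conclusion.** The point holds as an inconsistency in scan timing with a small, avoidable cost. Section 4.9.1 and the Table place the baseline PET before eligibility and randomisation; section 4.9.2 does not require this. On the 4.9.1 reading, people later found ineligible can be exposed to the tracer without yielding trial data. The documents do not show that this will happen or to how many: the range of about 1 to 7 unused scans per 20 randomised rests on assumed losses of 5% to 25%.

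The target of 5 per group among 20 is not secured by anything in the protocol. Its chance runs from about 1% under simple randomisation to certainty under one favourable blocked scheme, and the protocol does not say which applies. Severity is minor.

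**What to change.** - Amend section 4.9.1 and the Table of Assessments so that the baseline PET is done only once eligibility is confirmed and the participant is randomised, and before visit 1. Section 4.9.2 already allows this.
- Have the central web system of section 4.4.1 fill 5 PET places per arm, telling the site only whether the participant is to be scanned and not the arm. This makes 5/5/5/5 at baseline certain whatever the randomisation method, and no one found ineligible is scanned.
- State in section 5.5 D whether 20 counts people scanned at baseline or people with both scans. If it means pairs, the number of places per arm should allow for loss.

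The cost is tighter scheduling between randomisation and visit 1, and a quota added to an existing system. It is offset by fewer unused scans.

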5.6 Safety Analysis

The number and percentage of adverse events until the end of the study will be presented for each treatment group according to adverse event.

5.7 Additional Safety Analysis

Descriptive safety statistics for each treatment group will include the number of subjects, mean, standard deviation, minimum and maximum median for continuous variables, and frequencies and percentages for categorical variables.

Transcranial Near Infrared Laser Therapy in Subjects with Major Depressive Disorder: A Laser Dosing Study.

6. Ethical Review & Regulatory Considerations

6.1 Ethical Review

Prior to the start of the study, the investigator will obtain approval of the protocol and informed consent form from the IRB. Additional documentation may be required pending applicable local requirements. At least the following documentation should be obtained:

1. IRB / EC protocol approval.
2. IRB/EC approval of the informed consent form.
3. Approval of the annual renewal of the IRB/EC protocol (or at any other frequency when applicable, i.e. quarterly, semi-annually in accordance with the local IRB/EC standard operating procedure).
4. IRB/EC approval of any revisions to the Informed Consent Form or amendments to the protocol.

6.2 Regulatory Considerations

This study will be conducted in accordance with Good Clinical Practice (GCP) guidelines and other applicable regulatory requirements including, but not limited to:

- The Food and Drug Administration's (FDA) Investigational Device Exemption Regulations (21 CFR 812),
- FDA's Human Research Regulations (21 CFR 50, 54 and 56),
- Health and Human Services Regulations (DHHS) on human subjects research (45 CFR 46 Subpart A, B, C and D) and
- The International Conference on Harmonization (ICH) "Good Clinical Practice Guideline for Industry-E6: Consolidated Guideline".
- The regulation of clinical trials approved by DS 021-2017-SA.

6.3 ClinicalTrials.gov

The study will be registered and published on ClinicalTrials.gov (www.clinicaltrials.gov).

6.4 Monitoring Procedures

Monitoring will be conducted by the PI, who will periodically review laboratory results and clinical information. The PI will coordinate the different phases of protocol implementation, such as application and follow-up. The PI will be in frequent contact with the other staff members responsible for the delivery of the NIR-TLT and with Pthera LLC, who will loan the NIR-TLT device. We have minimized the risks potentially associated with NIR-TLT use by providing subjects and the operator with safety goggles or eye pads during NIR-TLT application and by requiring two methods of contraception (although NIR-TLT has not been associated with a teratogenic effect). We have also included treatment discontinuation rules based on the development of skin erythema or discomfort lasting more than 24 hours at TLT delivery sites (to avoid the risk of the subject having unknown skin photosensitivity)

Treatment will end for participants who experience temporary pain or discomfort during a treatment session that is present up to 24 hours after the end of the session.

Transcranial Near Infrared Laser Therapy in Subjects with Major Depressive Disorder: A Laser Dosing Study.

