4.4 Study Design

This study is a multicenter, randomized, sham-controlled, double-blind study on the use of transcranial continuous light therapy as a treatment for depressive symptoms in patients with major depressive disorder (MDD). Laser light therapy is tested in a strict parallel design.

This study will include 112 subjects randomly assigned to each of the four NIR-TLT treatment groups (28 subjects/group).

All subjects will receive three NIR-TLT treatments per week for 6 weeks and will complete a follow-up evaluation two weeks after treatment completion. All subjects and investigators (except the study statistician) will be blinded to treatment sequence assignment.

Energy will be administered at a wavelength of 808 nm, bilaterally to two frontal areas on the left and right side of the forehead, at or near electroencephalography sites F3 and F4. To maintain blinding, the treatment duration will be 429 seconds (7.15 minutes) for all groups. The treatment exposure (time during which the laser is active for the duration of the treatment) will be specific for each group, controlled by the device to normalize the treatment fluence of each active session per treatment location. Treatment will follow these specifications: wavelength 830 nm; average irradiance 350 mW / cm²; average fluence of 65.8 J / cm² (according to the parameters used in the ELATED-2 study at MGH with the Omnilux New U device) being the total fluence delivered: 3.6 kJ (bilateral) or 1.8 kJ (unilateral), either on the subject's forehead, at or near electroencephalography (EEG) sites F3 and F4.

The entire session (which includes the 429-second treatment and all procedures described in the "Study Visits" section) is estimated to take 30 minutes or less (Schiffer et al., 2009) (Lampl et al., 2007, Zivin et al., 2009). Additional time is needed to prepare the subject, fit the necessary protections (e.g., goggles), inspect the subject's skin, set up the NIR-TLT devices, and give the subject time to rest after irradiation. NIR-TLT treatment will only be administered by trained personnel who are on study staff. All personnel administering the treatment must pass laser safety training created by the American Institute for Medical Laser Applications and approved by the relevant Committees. The duration of irradiation will be decreased if clinically indicated, based on tolerability as needed.

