4.9.2 Treatment Visits 1 to 18 -Visits 1-6

Regular treatment visits (1 to 18) occur on non-consecutive days, 3 times per week for 6 weeks.

Purpose: The purpose of the treatment visits is to administer NIR-TLT and collect data to assess the effect of each of the NIR-TLT dose effects on MDD symptomatology (antidepressant effect) and tolerability.

Procedures: Trained study personnel will deliver NIR-TLT to study participants. Treatment visits are estimated to last approximately 429 seconds (7.15 minutes) and will take place in a dedicated NIR-TLT (laser safety) office. Only the subject and the staff administering NIR-TLT will be present during the session. The subject will lie comfortably on an examination bed or sit in a recliner, a cervical pillow (U-shaped) may be used for comfort and to prevent the helmet connector cables from being stepped on, bent or damaged. The NIR-TLT application sites (left and right forehead) will be inspected for skin lesions (e.g., lacerations or signs of inflammation) that might contraindicate treatment. During treatment sessions, a warning sign will be hung on the office door. Ideally the place where treatment is administered should be at a temperature of 25°C +/- 2°C.

Prior to treatment with the EXPi device, the subject's forehead is cleaned with 70% isopropyl alcohol, the cap is placed on the subject's head and secured, and the treatment beam locations are adjusted to match the F3 and F4 EEG sites (or very close if the site is covered by hair), the eyebrows may be used as a reference for placement of the lower edge of the helmet. The operator and subject are provided with appropriate laser safety glasses (optical density rating > 5.0 at 808 nm). Disposable caps may be used for hair control if necessary.

Trained personnel administering NIR-TLT will make every effort to never shine light into or near the subject's eyes. Patients and staff will wear safety glasses selected for the biophysical properties of NIR-TLT in accordance with Occupational Safety and Health Administration (OSHA) guidelines. The patient may sleep during the time of therapy administration.

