4.19 Subject Disposition Criteria

4.19.1 Withdrawal from the Study

Each subject and the investigator reserve the right at any time to terminate a subject's participation in the clinical investigation.

Possible reasons for withdrawal or removal from the study may include:

Transcranial Near Infrared Laser Therapy in Subjects with Major Depressive Disorder: A Laser Dosing Study.

1. The subject voluntarily withdraws consent.
2. The subject was ineligible according to the inclusion and exclusion criteria of the study.
3. The subject develops an adverse event that would not allow continuation in the study.
4. The subject has an adverse event that, in the opinion of the investigator, warrants withdrawal from the study. Pthera LLC must be notified within two business days.
5. The subject and/or the investigator make the decision that the subject should withdraw from the study.
6. Subject to death of participant.
7. Positive pregnancy test during eligibility procedures.
8. The subject misses one of the 3 scheduled sessions per week and it is not possible to make it up before the end of the week. When a subject withdraws or is withdrawn from the study, the following will be performed, if possible, at the study termination (exit) visit:
 - HAM-D-17
 - QIDS-C
 - CGI
 - C-SSRS
 - ADVERSE EVENT FORM
 - Concomitant Medication Form
 - ASQ (self-assessment)
 - SAFTEE-SI (self-assessment)
 - SDQ (self-assessment)

For all subjects who prematurely withdraw from the study, the date and reason for withdrawal will be documented.

4.19.2 *Loss of Follow-up*

If a center is unable to contact a subject or if the subject fails to appear for a visit, three documented telephone calls should be made, followed by a certified letter (or its equivalent, such as an e-mail). The certified letter should detail the need for the subject to appear for a visit, the center's failed attempts to contact the subject, and that failure to contact the center will cause the subject to be withdrawn from the study.

If the certified letter is returned to the center as undeliverable or the letter is delivered but the subject does not communicate with the center and no further contact is made with the subject or the subject's caregiver, then the subject will be considered lost to follow-up with the subject and suspended from the study. All attempts to contact the subject will be documented.

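### The missed-session rule in 4.19.2 withdraws participants whose laser treatment the protocol itself stops for safety, against 4.9.4, and so can lose their HAM-D17 at visits 9 and 18

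*Protocol*

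**What the plan says.** **Stopping treatment.** Sections 4.17.2 and 6.4.1 end laser treatment if erythema appears. They do not say whether the participant stays in the study. Section 6.4 describes the discomfort rule twice. One sentence refers to "treatment discontinuation rules based on the development of skin erythema or discomfort lasting more than 24 hours at TLT delivery sites". The next paragraph ends treatment for participants with "temporary pain or discomfort during a treatment session that is present up to 24 hours after the end of the session". Section 4.4 offers a milder response to tolerability problems: "The duration of irradiation will be decreased if clinically indicated, based on tolerability as needed".

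**Leaving the study.** Section 4.19.1 opens its list with "Possible reasons for withdrawal or removal from the study may include". Reasons 3 and 4 cover adverse events, and reason 4 rests on the investigator's opinion. Reason 8 is "The subject misses one of the 3 scheduled sessions per week and it is not possible to make it up" within the week. For anyone who leaves, "the following will be performed, if possible, at the study termination (exit) visit", and HAM-D-17 is among the items listed. Section 4.19.2 tolerates a delay of up to 72 hours if the week's three sessions can still be given. Otherwise it removes the participant from the study. That sentence is mandatory and has no exception.

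**Staying in the study.** Section 4.9.4 says participants will be urged to remain enrolled for follow-up even when laser treatment has ended.

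**Use of the data.** The primary comparison in 5.5 uses HAM-D17 at visits 1, 9 and 18. Section 5.5 also names an analysis by intention.

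**The concern.** A participant whose laser treatment is stopped under a safety rule cannot receive three sessions a week. Section 4.19.2 then removes that person from the study, although 4.9.4 wants participants to stay. Two sites could follow the same protocol and treat the same participant differently.

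At stake are the primary outcome scores of people who tolerated the treatment poorly. Missingness of that kind is tied to treatment, and an analysis by intention needs those scores. Section 4.20.1 lists erythema, pain, discomfort and heat at the application site as reported with this treatment, so the triggers are foreseeable. The data would be lost through an administrative rule and not because the participant declined assessment.

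The two discomfort wordings in 6.4 are a lesser matter. They affect how often treatment is stopped. The 24-hour point falls between visits, so site staff must apply the wording to what the participant reports.

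**Working it through.** **Step 1. The rules side by side, for a participant stopped for erythema or discomfort**

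| Section | What it does | Exemption for a safety stop |
|---|---|---|
| 4.17.2, 6.4.1, 6.4 | Ends treatment | Not applicable; silent on study participation |
| 4.17.3 | Says that an event warranting exit from the study leads to removal from treatment, so it mixes the two | None stated |
| 4.19.1 reasons 3 and 4 | Allow exit for an adverse event | Case-by-case; no link to the missed-session rule |
| 4.19.1 reason 8 | Missed session is a possible reason for exit | None |
| 4.19.2 | Fewer than three sessions in the week means exit | None |
| 4.9.4 | Urges continued enrolment after treatment stops | States the opposite outcome |

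No text ranks 4.19.2 against 4.9.4.

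**Step 2. Does a safety stop trigger 4.19.2?** The schedule is "Regular treatment visits (1 to 18) occur on non-consecutive days, 3 times per week for 6 weeks", so session k falls in week ceil(k/3). After a stop at any session from 1 to 17, that week or the next has fewer than three sessions, and the literal rule is met. A stop at session 18 does not meet it.

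**Step 3. Which primary scores are then outstanding?** For visits 1, 9 and 18, 4.9.2 says: "Prior to the NIR-TLT study, the staff will collect primary efficacy data from metric measurements and brain electrophysiology data". I read this as before that day's session.

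- Stop at sessions 1 to 8: visits 9 and 18 outstanding.
- Stop at sessions 9 to 17: visit 18 outstanding.
- Stop at session 18: neither.

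These are positions in the schedule, not counts of participants. Section 4.9.2 also lists HAMD-17 at treatment visits in general, whereas the Table of Assessments has it only at V0, V1, V9, V18 and V19. On either reading, nothing scheduled after withdrawal is collected.

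Assume the exit visit falls in the week of the stop. An exit score then precedes visit 18 by 6 − ceil(k/3) weeks: 5 weeks after sessions 1 to 3, falling by one week per block of three, to the same week after sessions 16 and 17. It does not substitute well for visit 18 after an early stop.

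**Step 4. Precision, for scale only.** Inputs from 5.3: difference 6.4, SD 7.091, alpha 0.05, power 90%, 20% loss. A one-sided two-sample t-test needs 22 per group; 22/0.8 = 27.5, rounded up to 28; 4 × 28 = 112, the plan's total. A two-sided test needs 27, then 27/0.8 = 33.75, so 34, and 4 × 34 = 136. The protocol does not state sidedness; the one-sided version is shown first because it matches 112.

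With the planned loss, each group has 28 × 0.8 = 22.4. The protocol gives no safety-stop rate, so suppose one active group loses a further share of its 28:

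| Further loss (assumed) | n active | Power, one-sided | Power, two-sided |
|---|---|---|---|
| 0% | 22.4 | 0.908 | 0.839 |
| 5% | 21.0 | 0.899 | 0.827 |
| 10% | 19.6 | 0.889 | 0.813 |
| 20% | 16.8 | 0.864 | 0.777 |

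This compares one active group with sham by t-test and does not represent the repeated-measures ANCOVA of 5.5.

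**Step 5. The two wordings in 6.4.** Pain that resolves 6 hours after a session meets the second wording, read literally, but not the first. The second also adds pain and drops the restriction to the delivery sites.

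**The case against.** The best case against this point is that 4.19.2 is about poor attendance. Its sentence stands under loss of follow-up, follows a sentence on tolerated delays, and speaks of compliance. A participant whose sessions the protocol cancelled has arguably not failed to comply. Reasons 3 and 4 of 4.19.1 already provide a route for adverse events that rests largely on judgment, the erythema rule stops treatment and not participation, and 4.9.4 addresses discontinued treatment directly. The sample size allows 20% loss, and 5.5 will examine dropout by group.

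Much of this is a fair account of what was probably meant, but it does not settle the text. Section 4.19.2 is mandatory and has no exemption. Reasons 3 and 4 do not override it. The paragraph holding the 4.9.4 sentence is mainly about clinical worsening and suicidality. Allowing for loss protects precision, and testing dropout rates describes the loss; neither recovers the scores.

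On 6.4 the objection largely succeeds. Discomfort still present at 24 hours is the likely meaning. It fits the stated purpose of detecting photosensitivity and the milder response in 4.4. A reader might infer that the second wording leaves participants exposed to harm. It does not: taken literally it errs towards stopping, so the cost is unnecessary stopping.

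**Conclusion.** The conflict is real: 4.19.2 read literally withdraws participants stopped for safety, and 4.9.4 wants them retained. It deserves correction because it can remove outstanding visit 9 and visit 18 HAM-D17 scores for reasons tied to tolerability, leaving only an exit score that may not be obtained.

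The size is unknown because the protocol gives no rate of erythema or discomfort stops. On the assumed range, the precision cost is a few points of power, probably small.

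A reader might go further and infer biased results, heavier loss in the active groups, or an underpowered trial. The documents do not support these. Hypothesis 2 in 4.1 expects no dose-dependent difference in side effects, and differential loss is possible but unquantified. Nor does the fact that stops at 17 of the 18 sessions leave a primary score outstanding measure the effect: nearly any early stop precedes a final-visit assessment.

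The conclusion rests on reading 4.19.2 as written and on HAM-D17 being taken before the session at visits 9 and 18. The 6.4 wording is a secondary, editorial correction.

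**What to change.** **In 4.19.1 and 4.19.2**, state that stopping laser treatment under a protocol safety rule is not study withdrawal and does not trigger the missed-session rule. State that these participants, if they consent, attend visits 9, 18 and 19 for HAM-D17, consistent with 4.9.4, and are included in the by-intention analysis.

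**In 6.4**, use one condition in both sentences, for example pain or discomfort still present 24 hours after the end of the session. The clinical threshold is for the sponsor and investigators to choose.

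**Cost.** Wording in three sections, and at most three assessment visits without treatment per stopped participant, all already scheduled. No change to sample size is needed on this account.
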